6.1 Potential Risks

Cholestyramine is a bile acid sequestrant that works by increasing the removal of bile acids from the body. The most common adverse reaction is constipation but most instances are mild, transient and controlled with conventional therapy. Other less frequent adverse reactions are abdominal discomfort, flatulence, nausea, vomiting and bleeding tendencies due to hypoprothrombinemia if use long term. Detailed information can be found on the drug leaflet attached at the appendix. Solomon et al. reported all patients tolerated cholestyramine without inordinate difficulty with 2 patients experienced hyperdefecation for a couple of days and all patients complained of the taste of the powders¹¹.

Prednisolone is a corticosteroid and work by modifying the body's immune to various conditions and decreasing inflammation. response In hyperthyroidism it reduces the conversion of T_4 to T_3 . The common adverse reactions include fluid retention, alteration in glucose tolerance, elevation in blood pressure, behavioural and mood changes, increased appetite and weight gain. There is a risk of hypothalamic-pituitary-adrenal axis suppresion and Cushing's syndrome if given long term. It may increase the risks related to infection but rate of occurrence increases with the dose of steroids. There may be an increase risk of peptic ulcer disease. If used long term may decrease bone density. In a meta analysis, the use of prednisone 35 mg daily for a mean 64 days increased the risk for diabetes (OR 1.7 (1.1-2.6) P= 0.02), hypertension (OR 2.2 (1.4-3.8) P =0.01), dermatologic effects (OR 4.5 (3.5-5.7) P= 0.001) but was not statistically significant association for peptic ulcer, bacterial sepsis, osteoporosis, psychosis and tuberculosis¹⁹. Steroids may cause muscle weakness from renal potassium loss and myopathy if taken long term but there are case reports of thyrotoxic periodic paralysis soon after glucocorticoid administration²². The detailed information regarding risks and adverse reactions to prednisolone can be found in the drug leaflet attached in the appendix.

The immediate risks foreseeable in this study would be the risk of iatrogenic hypothyroidism. However this risk is closely monitored and the event of

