7 OBJECTIVES

7.1 Primary objectives:

1. To assess the efficacy between Cholestyramine plus standard treatment (Carbimazole plus Propanolol), Prednisolone plus standard treatment and standard treatment alone in subjects with overt hyperthyroidism

7.2 Secondary objective(s):

1. To assess the safety profile of Cholestyramine plus standard treatment, Prednisolone plus standard treatment and standard treatment alone.

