9.9 Assessment of safety

Safety data will be analysed for the data collected throughout intervention period and up to follow up period. The following endpoints will be collected:

- Number of subjects with adverse effects during the intervention period and follow up period (total duration 6 weeks)
 - Subjects will be asked to report about adverse reactions (specified in the protocol) at 2 weeks, 4 weeks of intervention period and 2 weeks after end of study treatment period.
 - Number of subjects with serious adverse events during intervention period and follow up period (total duration 6 weeks)
 - Subjects will be asked to report about SAE immediately during the intervention period and follow up period

Safety and tolerability assessments will consist of:

- Regular performance of physical examinations
 - 1. BP, PR, Temperature, Weight (kg)
- Regular monitoring of laboratory tests
 - FPG/ RPG, Electrolytes (Na⁺, K⁺, Urea, Creatinine), FT₄, FT₃, TSH
- Monitoring and recording all adverse reactions and serious adverse events

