11.1.2 Baseline visit (Week 0, Visit 2)

- Subjects who are eligible for the study after reviewing both inclusion and exclusion criteria will be called up for a baseline visit no longer than 1 weeks from screening visit.
- 2. Perform baseline measurements of vital signs (BP, HR, Temperature) and anthropometric measurements (Height (cm), Weight (kg) and BMI
- 3. Perform complete medical history and physical examination if not done during screening visit
- 4. Record any concomitant medications
- 5. The following baseline tests will be performed (Total of 6 mls of blood will be sampled). Thyroid function test and TRAb levels will be sent to central lab (Gribbles laboratory) whereas the other tests will be conducted at respective site.
 - a. Free T₄, Free T₃, TSH
 - b. TRAb levels
 - c. UPT (For all women of childbearing age)
 - d. ECG
 - e. ECHO if evidence of thyrotoxic cardiomyopathy
- 6. Complete relevant section/page of the CRF.
- 7. Subject who has fulfilled all inclusion and exclusion criteria and has completed baseline assessment will proceed to randomisation into any of the 3 treatment groups on the **same day**.
- 8. Refer to the study activities table below

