13.2.2 Efficacy Analysis

1. For the primary objectives, all comparisons of means between treatment will be analysed using one-way ANOVA and all pairwise comparisons of proportions will be analysed by using two-sided Z test and 95% confidence interval of the estimated difference will be calculated. Alpha level will be set at 0.05 and no adjustment will be made for the multiple pairwise comparisons. Analysis will be based on intention to treat and per protocol analysis.

2. For secondary objectives, all comparisons of means between treatment will be analysed using one-way ANOVA and all comparison of proportions will be analysed using chi-square test of independence.

Alpha level will be set at 0.05. Analyses will be based on safety set analysis.

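### Safety means are assigned a one-way ANOVA with no baseline term, no adjunct-versus-standard estimate and no stated variable, visit or scale, which gives up precision that data already collected could supply, chiefly for weight

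*Combined protocol and SAP*

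**What the plan says.** The single secondary objective (section 7.2) is "To assess the safety profile of Cholestyramine plus standard treatment, Prednisolone plus standard treatment and standard treatment alone". Its analysis is section 13.2.2 item 2, repeated in the synopsis:

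- For means: "For secondary objectives, all comparisons of means between treatment will be analysed using one-way ANOVA".
- For proportions: "all comparison of proportions will be analysed using chi-square test of independence".
- Level and population: "Alpha level will be set at 0.05. Analyses will be based on safety set analysis".

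Item 1 of the same section promises pairwise comparisons of proportions and a 95% CI of the difference for the primary objective. Item 2 promises neither for safety.

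Section 9.9 defines the safety endpoints as counts, the first being "Number of subjects with adverse effects during the intervention period and follow up period (total duration 6 weeks" and the second the matching count for serious events. Separately, as safety and tolerability assessments, it lists "BP, PR, Temperature, Weight (kg" together with fasting or random glucose, electrolytes, creatinine and thyroid function.

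Pre-treatment values exist for all of these. Section 11.1.2 says "Perform baseline measurements of vital signs (BP, HR, Temperature) and anthropometric measurements", and the Study Activities Table shows weight and vital signs at weeks -1, 0, 2, 4 and 6. Glucose and electrolytes are taken at screening and at weeks 2, 4 and 6.

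Section 6.1 includes "elevation in blood pressure, behavioural and mood changes, increased appetite and weight gain" among the common reactions to prednisolone. Section 10.1.1 makes diabetes and hypokalemia mandatory events with laboratory cut-offs. Weight gain and raised blood pressure are not on that list and have no cut-off.

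**The concern.** A one-way ANOVA has no place for a covariate. If it is run on the week 2, 4 or 6 values themselves, all between-person spread stays in the error term. Weight differs between adults by far more than four weeks of treatment could change it, so the subject's own earlier weight would explain most of that spread. The plan collects that value but names no use for it.

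The three-group F test also does not answer the question a reader will ask: how much does each adjunct differ from standard treatment, and how precisely is that known?

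This matters most for weight and blood pressure. Harms to glucose and potassium have a second route into the report through the event cut-offs. For weight and blood pressure the comparison of means is the main objective check, in an open-label trial of a drug whose safety as an adjunct section 6 describes as not yet known.

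**Working it through.** **Plan's own figures.** Section 13.1 sizes the trial on the primary objective only, so there is no stated power for any safety mean to reproduce. The number per arm does reproduce closely. For 40% v 70%, two-sided 0.05, 80% power and pooled variance, n = [1.96·√(2·0.55·0.45) + 0.8416·√(0.4·0.6 + 0.7·0.3)]² / 0.3² = 41.97, against 41 stated. Exact enumeration at 41 gives 81.3%. With 10% dropout, 41/0.9 = 45.6, against 45 stated. I use 45 per arm.

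**Assumptions.** The documents give no SD, shift or correlation with baseline (r). I assume a shift d in Group 2 only. For weight, d = 2 kg, SD 10 to 15 kg, r 0.90 to 0.98. For systolic pressure, d = 5 mmHg, SD 15, r 0.5 to 0.7. For potassium, d = 0.2 mmol/L, SD 0.4, r 0.2 to 0.6.

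**Formulas.**
- Raw omnibus ANOVA: noncentral F with 2 and 132 df, critical value 3.065, λ = 45·(2/3)·d²/SD².
- Baseline-adjusted Group 2 v Group 3 contrast: residual SD s = SD·√(1 − r²), SE = s·√(2/45) = 0.2108·s, power ≈ Φ(d/SE − 1.96).
- Change score: the same F calculation with SD·√(2(1 − r)).

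**Weight, 2 kg shift.** λ = 1.20, 0.83 and 0.53 for SD 10, 12 and 15.

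| SD (kg) | Raw ANOVA | Adjusted, r 0.90 | r 0.95 | r 0.98 |
|---|---|---|---|---|
| 10 | 15% | 59% | 86% | over 99% |
| 12 | 12% | 44% | 72% | 98% |
| 15 | 9% | 31% | 53% | 89% |

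Worked cell (SD 12, r 0.95): s = 12·√(1 − 0.9025) = 3.75, SE = 0.79, d/SE = 2.53, power = Φ(0.57) = 72%.

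At SD 12 the pairwise difference detectable with 80% power is 2.80·12·0.2108 = 7.1 kg raw. Adjusted, it is 2.2 kg (r 0.95) or 1.4 kg (r 0.98).

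**Sensitivity.** For a 1 kg shift at SD 12, raw power is 7%. Adjusted power at r 0.95 is 24% (1/0.79 = 1.27). With 41 evaluable per arm and a 2 kg shift, the raw range is 9 to 14%.

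**Systolic pressure.** λ = 45·(2/3)·25/225 = 3.33, raw 35%. Adjusted: r 0.5, SE = 2.74, d/SE = 1.83, 45%; r 0.7, SE = 2.26, d/SE = 2.21, 60%.

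**Potassium.** λ = 45·(2/3)·0.04/0.16 = 7.5, raw 68%. Adjusted: r 0.2, SE = 0.0826, d/SE = 2.42, 68%; r 0.6, SE = 0.0675, d/SE = 2.96, 84%.

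**If changes were meant instead.** A one-way ANOVA of weight change at SD 12 has 42%, 73% or 99% power for r 0.90, 0.95 or 0.98, about the same as ANCOVA. For potassium at r 0.2, SD·√1.6 = 0.506 and λ = 4.69, which gives 47%, below the raw 68%. Change scores lose power when r is under 0.5; ANCOVA does not.

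**Cost of the omnibus form.** Raw weight at SD 12: omnibus 11.6%, pairwise t test 12.2%. Almost no power is lost.

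**The case against.** A reader might infer that the plan specifies raw values. It does not. Item 2 defines no dependent variable, and an ANOVA of changes would fit the same sentence. Nor does it name weight, blood pressure, potassium or glucose as means to be compared. The defined safety endpoints are counts, which go to chi-square. This stands: what can be criticised is the silence, together with the absence of a baseline term, contrast and interval.

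A reader might also infer that steroid effects would be missed and the adjunct then declared safe. The documents do not support that. Randomisation keeps the unadjusted comparison unbiased. Diabetes and hypokalemia are caught by cut-offs. Section 10.2 has all adverse events documented, including those found on examination, although for weight and blood pressure this depends on someone recognising the event. Nothing in the plan equates a non-significant ANOVA with safety, and 13.1 promises no power for safety.

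The size also rests wholly on assumed values. Weight is the extreme case, and even adjusted power falls to 31% at SD 15 and r 0.90.

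Section 13.1 says the analysis treats the three arms much like separate trials, which leans towards a pairwise reading. Item 2 still gives no contrast or CI for safety, so that gap remains.

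Two cautions about ANCOVA also stand. Glucose may be fasting or random, so adjusting one type for the other is hard to interpret. And section 6 lists weight loss as a sign of hyperthyroidism, so a between-arm weight gain may partly reflect faster thyroid control.

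**Conclusion.** The point holds as an underspecified and inefficient analysis, of minor to moderate importance. The only method named for safety means leaves out baselines that the trial collects and yields no adjunct-versus-standard estimate, and the plan leaves variable, visit and scale open.

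If raw values are used, the loss is large for weight, modest for systolic pressure and small to modest for potassium. All of this is conditional on the assumed SDs, shifts and correlations. If changes are used, the loss for weight largely disappears, but power can fall for weakly correlated measures such as potassium.

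The three-group test matters for the missing estimate and interval, not for power. The ANOVA is valid, and the case for ANCOVA is precision. It does not follow that harms would be missed.

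**What to change.** In section 13.2.2 item 2 and the matching line of the synopsis:

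1. Name the safety variables to be compared as means, at least weight, blood pressure and potassium, and the visits (weeks 2, 4 and 6).
2. Replace one-way ANOVA by ANCOVA at each visit, with treatment group and the subject's own pre-treatment value: visit 2 for weight and blood pressure, screening for potassium.
3. Report the Group 1 v Group 3 and Group 2 v Group 3 adjusted differences, each with a 95% CI.
4. For glucose, adjust only where baseline and follow-up samples are of the same type, both fasting or both random. Otherwise rely on the diabetes event already defined in 10.1.1.
5. State that weight differences will be read alongside thyroid status at the same visit.

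The cost is a few lines of plan text and SPSS syntax. No new visit, sample or patient is needed.

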14 ADMINISTRATIVE MATTERS

14.1 Notification of regulatory authority(ies)

All necessary arrangements for the registration and approval of this study with the responsible authorities and the disposition of the required data and document will be undertaken by the Principal Investigator.

14.2 Notification of primary care physician

The General practioner or primary care physician will be informed of the subject's involvement in this study. This is so that if the patients need to see their own physician for any reason, the physician will be aware that they are taking a studydrug.

14.3 Study initiation

The study will begin only after getting the approval from MREC.

14.4 Protocol deviation

Any protocol deviation will be documented by the Investigator with rectification as soon as possible. The investigator should be notified immediately. With the exception of emergency situations, no changes or deviations in the conduct of this protocol will be permitted without the prior approval from MREC. In the event of any emergency, the investigators will institute any medical procedures deemed appropriate. All such procedures must be promptly reported to MREC.

14.5 Study documentation

All documentation will be maintained. These documents are Essential Documents and Source Documents.

14.5.1 Essential documents

These are documents that permit evaluation of the study and the quality of the data produced. The Essential Documents are:

- Signed protocol amendments
- Sample CRFs
- MREC approval letter
- Informed consent form
- CV of investigator and co-investigator
- Investigational product accountability and shipping records
- Other appropriate documents in accordance with GCP guidelines.

The investigator will maintain an Investigators Study File. This file shall be used to facilitate and ensure filing of all relevant and Essential Documents during and after the study. The investigator will be responsible for keeping the Investigator's Study File updated and ensuring that all required documents are filed. The file will be inspected during monitoring visits.

14.5.2 Source documents

These are original hospital records, clinical charts, subject screening checklist, original laboratory reports, pharmacy dispensing records, and records kept at the pharmacy, at the laboratories and at medico-legal departments involved in the study. All source documents would be kept confidential of personal information.

The investigator must maintain source documents for each patient in the study. All information on CRFs must be traceable to these source documents:

- Patient identification list
- Curriculum vitae

14.6 Patient identification list/Enrolment log

An enrolment log will be maintained that contain a list of all enrolled patients containing the full name, date of birth, date of enrolment, and the randomization number. The list has to show an unequivocal study identification number. The list will be filed in the Investigator's Study File on site.

14.7 Curriculum vitae

The investigator will provide curriculum vitae showing his/her experience in the area of the proposed study. These should be filed at CRC as well as in the Investigator's Study File on site.

14.8 Retention of documents

All study documents will be or at least 3 years after completion or discontinuation of the study.

If the investigator moves or retires, he/she must nominate someone in writing to be responsible for archiving. Archived data may be held in microfiche or electronic record, provided a back up exists and a hard copy can be obtained from it if required.

If the investigator cannot guarantee this archiving requirement at the study site for any or all of the documents, special arrangements must be made with CRC to store these in a sealed container(s) outside of the site so that they can be returned sealed to the investigator in case of a regulator audit. Where source documents are required for the continued care of the subject, appropriate copies should be made for storage outside of the site.

14.9 Finance

The study will be funded by the Ministry of Health Malaysia to support the work of the investigator and supply the required investigational product for the study.

14.10 Study Termination and Site Closure

The study may be terminated early if there is:

- Deliberate violation of the signed protocol
- The incidence and/or severity of adverse events in this or other studies indicate a potential health hazard caused by the treatments under trial.

14.11 Confidentially

The investigator agrees that all information will be kept strictly confidential.

14.12 Publication policy

The investigator shall have the right to publish or permit the publication of any information or material relating to or arising out of the work. Publishing will protect the confidentialty of subjects' personal information.

14.13 Anticipated subject accrual and duration of the study

This study is expected to start in April 2017. The projected study timetable for the study is as follows:

- First patient enrolled is expected in March/ April 2017
- Last patient enrolled is expected in December 2017
- The last patient enrolled is projected to complete the treatment period in December 2017

16 APPENDICES

- Declaration of Helsinki
- Study Procedures
- Questionnaire and CRF (*if applicable*)
- Investigational product labels
- Elements of informed consent
- Sample informed consent form (in different languages)
- Patient information sheet (in different languages)
- Letter of indemnity
- Investigators' curriculum vitae
